#### 6.1.1 Definitions of Solicited AEs:

The adverse event (AE) most likely to occur in this study is bladder discomfort. This is a study outcome and therefore will not be reported. Other potential AEs are listed in Table 2. As with bladder discomfort these AEs will be recorded but not reported.

Relationship	Description
POSSIBLE	Urinary leakage
POSSIBLE	Bladder discomfort
POSSIBLE	Catheter blockage
POSSIBLE	Haematuria
POSSIBLE	Accidental Removal
Yes	Valve not opening

[figure not shown]
Table 2 Solicited Adverse Events (AEs)

6.1.2 Specific actions following Adverse Events:

Participant advised to stop using the valve:

- If symptoms suggest a urinary tract infection advise the participant to send a urine sample to their GP
- Participant reverts to usual form of urinary catheter
  - URINARY CATHETER 'FILL AND FLUSH' VALVE: SAFETY, EFFECTIVENESS, ACCEPTABILITY AND FEASIBILITY TRIAL Protocol Version 3.1 20/08/2019 - IRAS: 245818 - ERGO: 41448

• If symptom recurs, participant to be withdrawn

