#### 4.3 Outcomes

4.3.1 Primary outcomes:

Safety: Reliability

• Valve opening - Proportion of observations of automatic valve opening before bladder capacity (500ml or less) is reached - as measured by bladder scanner (Valve Log)

Safety: Effectiveness

- Bladder emptying proportion of valve voids with residual urine <100ml as measured by bladder scanner (Valve Log)
- Participant report (Valve self-report questionnaire) *Comfort*
- Participant report (Valve self-report questionnaire)

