#### Testing Procedure

With the participant sitting (except when transferring to and lying on the bed for bladder scanning):

- 1. Participant puts on pad with pants to secure it in place
- 2. Record participant's self-reported bladder sensations
- 3. Scan bladder and record volume in Valve Log.
- 4. Research nurse fits the lowest pressure valve according to manufacturer's instructions for use and attach a drainage bag for urine collection. Record Valve Batch/Serial Number in Valve Log.
- 5. Record participant's self-reported bladder sensations in valve log
- 6. Scan bladder and record volume in valve log
- 7. If the valve remains open with urine draining freely, replace with the next level pressure valve (up to 3 valves) until free drainage has ceased and the valve remains closed. Record Valve Batch/Serial Number in Valve Log.

URINARY CATHETER 'FILL AND FLUSH' VALVE:

SAFETY, EFFECTIVENESS, ACCEPTABILITY AND FEASIBILITY TRIAL Protocol Version 3.1 20/08/2019 - IRAS: 245818 - ERGO: 41448

- 8. Participant to lie on bed for hourly bladder scanning (record time and volume in Valve Log) until bladder volume is >400mls or the participant experiences bladder discomfort or the valve automatically opens. Record participant's bladder sensations before each scan and:
  - a. If the volume is >400mls or the participant is experiencing discomfort
    - i. Ask the participant to contract abdominal muscles, press down on abdomen or bear down as if trying to pass urine to increase bladder pressure.
    - ii. If the valve opens, proceed as below (b).
    - iii. If the valve does not open, disconnect the valve, attach a new drainage bag and allow the bladder to drain. Stop the trial for that participant.
  - b. If the valve automatically opens:

Southampton

- i. Record the amount of urine voided
- ii. Scan the bladder for any residual volume
- 9. If the valve has opened with a urine volume of less than 500ml, repeat process 7 & 8 at 1 hourly intervals for 5 hours. If the valve did not open before bladder volume reached 500ml, stop testing at this point.

Participants will be requested to drink a minimum of 500mls of fluids over the first two hours, then a minimum of 150mls per hour for the next 3 hours. They will be given a choice of drinks. After testing has ended for that day, participants will be given a new manual valve and/or drainage bag as per usual use.

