#### Testing Procedure

With the participant sitting (except when transferring to and lying on the bed for bladder scanning):

- 10. Participant puts on pad with pants to secure it in place
- 11. Record participant's self-reported bladder sensations
- 12. Scan bladder and record volume in Valve Log
- **13**. Participant fits the lowest pressure valve according to manufacturer's instructions for use and attach a drainage bag for urine collection.
- 14. Record Valve Batch/Serial Number in Valve Log.
- 15. Record participant's self-reported bladder sensations in valve log
- 16. Scan bladder and record volume in valve log
- 17. If the valve remains open with urine draining freely, replace with the next level pressure valve (up to 3 valves) until free drainage has ceased and the valve remains closed. Record Valve Batch/Serial Number in Valve Log.
- 18. Participant will be asked to stand, walk around and cough at specific intervals as per flowchart in appendix C.

URINARY CATHETER 'FILL AND FLUSH' VALVE:

SAFETY, EFFECTIVENESS, ACCEPTABILITY AND FEASIBILITY TRIAL Protocol Version 3.1 20/08/2019 - IRAS: 245818 - ERGO: 41448

- 19. Record participant's bladder sensations before each scan and:
  - a. If the volume is >400mls or the participant is experiencing discomfort
    - i. Ask the participant to contract abdominal muscles, press down on abdomen or bear down as if trying to pass urine to increase bladder pressure.
    - ii. If the valve opens, proceed as below (b).
    - iii. If the valve does not open, disconnect the valve, attach a new drainage bag and allow the bladder to drain. Stop the trial for that participant.
  - b. If the valve automatically opens:
    - i. Record the amount of urine voided
    - ii. Scan the bladder for any residual volume

As with Day 1, participants will be requested to drink a minimum of 500mls of fluids over the first two hours, then a minimum of 150mls per hour for the next 3 hours. They will be given a choice of drinks. After testing has ended for that day, participants will be given a new manual valve and/or drainage bag as per usual use.

If a participant has to stop testing during Day 1 they will not be eligible for any further testing. All data will be collected by an appropriately trained research nurse (RN).

**Valve Questionnaire**: After all testing is completed; participants will complete a Valve Questionnaire to assess the valve for comfort.

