## 5.9 Data Analysis:

5.9.1 Clinical

Descriptive statistics will be used to summarise

- Demographics of participants
  - Total number and percentage of men and women will be reported
  - Total number and percentage from each age groups will be reported
- Bladder volume when the valve opened and residual bladder volume when the valve closed while undertaking different activities
  - The range and mean average of the volume of urine in the bladder at each valve opening for each activity will be reported.
- Questionnaire findings (for each occasion the questionnaire is completed)
  - For binary questions (yes/no), the total number and percentage of each answer will be recorded
  - For scale response questions, the total and percentage number of participants answering each response (e.g. Very comfortable, Quite comfortable, neither comfortable or uncomfortable, Quite uncomfortable, Very uncomfortable) will be reported.

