## 6.1 Adverse event (AE) recording & reporting:

For purposes of this protocol:

- All AEs will be recorded at participant visits or ad hoc phone calls with the participant and the research nurse and categorised as to expectedness, relatedness and severity.
- All non-solicited AEs will be reported. Depending on the nature of the event, the reporting procedures below should be followed. Any questions concerning adverse event reporting will be directed to the Chief Investigator in the first instance.
  - o Adverse Events form is sent to the Chief Investigator
  - Severity of AEs will be graded on a three-point scale (mild, moderate, and severe).
  - Relation (causality) and seriousness of the AE to the treatment will be assessed by the Chief Investigator.

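### Bladder discomfort is kept out of adverse-event reporting as a study outcome, but discomfort recorded during individual fills enters no outcome in section 4.3 and no summary in section 5.9.1

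*Protocol*

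**What the plan says.** Section 6.1.1 identifies bladder discomfort as the adverse event most likely to occur and gives one reason for not reporting it: "This is a study outcome and therefore will not be reported". It treats the other solicited events in its Table 2 the same way: "As with bladder discomfort these AEs will be recorded but not reported".

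Comfort is a primary outcome in section 4.3.1, with the Valve self-report questionnaire as its only source. In that section the Valve Log supplies valve opening and residual volume. Section 4.3.2 lists the questionnaire for acceptability and two quality-of-life tools, but not the log. The section 2 summary differs: there the Valve log is one of three patient-reported secondary end points.

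The questionnaire comes at the end. Section 5.6.2 says that, once testing is finished, "participants will complete a Valve Questionnaire to assess the valve for comfort". Sensations are collected much more often. On both days they are noted before fitting (steps 2 and 11), after fitting (steps 5 and 15: "Record participant's self-reported bladder sensations in valve log") and during filling (steps 8 and 19: "Record participant's bladder sensations before each scan and").

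Section 5.9.1 plans summaries of demographics, bladder volumes and questionnaire answers.

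**The concern.** The exemption in 6.1.1 works only if discomfort reaches the results as an outcome. The stated route is a questionnaire completed after testing. The record made at the time, which sits beside the bladder volume and the identity of the valve, has no stated route to a result.

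This bears on the trial's own aims. Section 4.2 asks whether filling and automatic draining is a comfortable process. Section 3.2 wants early evidence on which valve variant works and in what circumstances. As the protocol describes it, an end-of-testing questionnaire does not tie discomfort to a fill, a volume, a variant or a day, whereas the log can.

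Coverage is a second issue. Discomfort leads to a straining attempt and, if the valve stays closed, to stopping the participant. Someone stopped on Day 1 has no further testing, and the questionnaire is described only in the Day 2 section. Whether such a participant completes it is not stated. Those most likely to have had discomfort could therefore be missing from the one planned comfort summary.

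**Working it through.** The protocol gives no figure to reproduce, so the check follows bladder discomfort from collection to result.

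1. **Adverse-event route.** Discomfort is recorded: "All AEs will be recorded at participant visits or ad hoc phone calls with the participant and the research nurse". Section 6.1 also has it categorised. Section 6.1.1 then exempts it from reporting because it is an outcome, and section 5.9.1 lists no adverse-event summary.
2. **Outcome route, section 2.** The Valve log is a patient-reported secondary end point. The participant-reported content that section 5.6 describes for the log is bladder sensation, so the summary appears to intend those data as an outcome.
3. **Outcome route, section 4.3.** Comfort uses the questionnaire only. The log is used for opening and residual volume and is absent from 4.3.2. The end point named in section 2 has no counterpart here.
4. **Analysis route, section 5.9.1.** Volumes are summarised by activity and questionnaires by response. Sensations and discomfort do not appear.
5. **Result.** Followed as written, the protocol produces no result for discomfort during fills, although the data are collected.

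**Amount of data involved.** Day 1 has one entry before fitting, one after fitting and one before each of five hourly scans: 1 + 1 + 5 = 7. Over 16 participants that is 7 x 16 = 112. The Day 2 scan times are in a flowchart that is not shown. If Day 2 also has five scans, the total is 7 x 2 x 16 = 224. Early stopping lowers this number and extra scans would raise it. Steps 2 and 11 do not name the log as the place of recording. The count shows scale only; the finding does not depend on it.

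**Coverage of the safety review.** Section 5 has the safety data of the first 4 participants reviewed, which is 4/16 = 25% of the sample. No summary of discomfort is stated for all 16.

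**The case against.** A reader might infer that discomfort disappears from the trial, or that the reason in 6.1.1 is false. The documents support neither.

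- **Discomfort is an outcome in aggregate.** Comfort is primary in 4.3.1 and its questionnaire answers are tabulated in 5.9.1. The reason in 6.1.1 is therefore incomplete, not untrue.
- **The events are not lost.** In section 6, reporting means sending events onward; recording and categorisation still apply. The interim review includes the first four participants' safety data, and section 6.3 counts new pain that persists after valve removal as clinically significant.
- **It would be wrong to say that no outcome uses the log.** Section 4.3.1 uses it for two primary measures, and section 2 names it as patient-reported.
- **The questionnaire cannot be called a single recalled rating.** It is not shown, and 5.9.1 speaks of "Questionnaire findings (for each occasion the questionnaire is completed").
- **Sensation is not the same as discomfort.** No response format is given, and an entry may describe ordinary fullness.

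The strongest objection is that tables of sensations can be left to a statistical analysis plan. That is fair, and the missing table alone would not be a finding. What stands is that the protocol's own sections disagree on whether participant report in the Valve Log is an end point, while 6.1.1 relies on discomfort being one. An analysis plan should not have to decide which section defines the outcomes.

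**Conclusion.** The point holds as an inconsistency between sections 2, 4.3, 5.9.1 and 6.1.1. Its consequence is that the protocol states no result for discomfort during individual fills, on a question that is both an objective and a primary outcome domain. The change should be made. It is not a safety failure, because the events are recorded and the early ones reviewed.

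The conclusion rests on two readings. The first is that the log's patient-reported content is the bladder sensations, the only such content described. The second is that the analysis list in 5.9.1 is meant to cover the clinical data. How far the comfort result would change cannot be estimated, because the protocol gives no expected rate of discomfort.

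**What to change.** - **Section 4.3.2:** list discomfort recorded in the Valve Log as a secondary patient-reported outcome, matching section 2. Keep the questionnaire as the primary comfort measure in 4.3.1.
- **Section 5.9.1:** add one descriptive table of the number and percentage of all participants fitted with a valve who have discomfort recorded with the valve in place, by day, group and valve variant. Show the bladder volume at that time and the pre-fitting sensation alongside. Groups have 8 participants, so one person is 1/8 = 12.5%; give counts with every percentage.
- **Definition:** state which entries count as discomfort rather than ordinary sensation. The discomfort condition already written into steps 8a and 19a can serve, with no change to the procedure.
- **Steps 2 and 11:** say that the pre-fitting entry goes in the log.
- **Section 5.6.2:** state whether participants stopped on Day 1 complete the questionnaire, and give its denominator.
- **Section 6.1.1:** refer to the outcome in 4.3, so that the exemption points to a defined result.

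The cost is a few lines of wording and one table from data already collected. The downside is that comfort may look less favourable than the questionnaire alone would show.

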#### 6.3 Safety Stopping Criteria

If none of the first 4 participants have successfully completed protocol (in either day 1 or day 2), the trial will be stopped.

In case of occurrence of an SAE considered to be at least possibly related to trial or in case of two severe or clinically significant AEs considered to be at least possibly related to the trial, the study will be halted. The trial will only be re-started following an internal review of safety.

Clinically significant adverse events are:

- Accidental dislodgement of urinary catheter during intervention.
- The requirement to change the urinary catheter.
- New bladder or pelvic pain not resolved by the removal of the valve.

URINARY CATHETER 'FILL AND FLUSH' VALVE: SAFETY, EFFECTIVENESS, ACCEPTABILITY AND FEASIBILITY TRIAL

Protocol Version 3.1 20/08/2019 - IRAS: 245818 - ERGO: 41448

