## **12. APPENDICES**

#### **APPENDIX A – ADVERSE EVENTS DEFINITIONS**

Southampton

Any untoward medical occurrence in a subject to whom a study intervention or procedure has been administered, including occurrences which are not necessarily caused by or related to that intervention. An AE, therefore, does not necessarily have a causal relationship with the treatment. In this context, "treatment" includes all interventions administered during the course of the study. Medical conditions/diseases present before starting study treatment are only considered adverse events if they worsen after starting study treatment.

**Related AE:** An AE that results from administration of any of the research study procedures. All AEs judged by either the reporting investigator or the sponsor as having reasonable causal relationship to a study procedure qualify as 'related adverse events'. The expression "reasonable causal relationship" means to convey in general that there is evidence or argument to suggest a causal relationship.

Causality: The assignment of the causality should be made by the investigator responsible for the care of the participant using the definitions in the table below. All adverse events judged as having a reasonable suspected causal relationship to a study procedure (i.e. definitely, probably or possibly related) are considered to be related adverse events. If any doubt about the causality exists, the local investigator (PI) should inform the Chief Investigator. In the case of discrepant views on causality between the investigator and others, all parties will discuss the case. In the event that no agreement is made, the main REC and other bodies will be informed of both points of view.

Relationship	Description		
Unrelated	There is no evidence of any causal relationship		
Unlikely	There is little evidence to suggest there is a causal relationship (e.g. the event did not occur within a reasonable time after administration of the study procedure). There is another reasonable explanation for the event (e.g. the participant's clinical condition, other concomitant treatment).		
Possible	There is some evidence to suggest a causal relationship (e.g. because the event occurs within a reasonable time after administration of the study procedure). However, the influence of other factors may have contributed to the event (e.g. the participant's clinical condition, other concomitant treatments).		

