#### Severity (intensity) of Adverse Events and Adverse Reactions

Severity of all AEs will be graded on a three-point scale of intensity (mild, moderate, severe):

- Mild: Discomfort is noticed, but there is no disruption of normal daily activities.
- Moderate: Discomfort is sufficient to reduce or affect normal daily activities.

• Severe: Discomfort is incapacitating, with inability to work or to perform normal daily activities.

[figure not shown]
An AE may be severe but not serious.

#### APPENDIX B – TRIAL PROCEDURES: DAY 1

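### Section 6.1.1 exempts every Table 2 adverse event from reporting whatever its severity, yet some of these events count towards the two-event halt in section 6.3

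*Protocol*

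**What the plan says.** **Reporting exemption.** Section 6.1.1 names bladder discomfort as the likeliest adverse event and says of it: "This is a study outcome and therefore will not be reported". It then extends the exemption to the rest of Table 2: "As with bladder discomfort these AEs will be recorded but not reported". Table 2 has six rows: urinary leakage, bladder discomfort, catheter blockage, haematuria, "Accidental Removal", and the valve not opening.

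**Halting rule.** Besides a related serious adverse event, section 6.3 gives a second trigger: "in case of two severe or clinically significant AEs considered to be at least possibly related to the trial, the study will be halted". It defines three events as clinically significant. The first is "Accidental dislodgement of urinary catheter during intervention"; the others are the need for a catheter change, and new bladder or pelvic pain that persists once the valve is off.

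**Grading.** Appendix A states that "Severity of all AEs will be graded on a three-point scale of intensity". Its top grade reads: "Severe: Discomfort is incapacitating, with inability to work or to perform normal daily activities". It also notes that a severe event need not be a serious one.

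**Route.** Section 6.1 has all adverse events recorded and categorised, but reports only the non-solicited ones. The reporting step it describes is an Adverse Events form to the Chief Investigator.

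**The concern.** The adverse event trigger in 6.3 needs two events. They may occur in different participants on different days, so somebody has to learn of each one promptly and keep the count. Section 6.1.1 removes the reporting step for a class of events that includes some the count depends on. It does so whatever the severity and without referring to 6.3.

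If staff follow 6.1.1 as written, two severe non-serious solicited events could sit in two case report forms while testing continues. This is a first-in-human study of a device without a CE mark. The group tested last, the free-drainage users, is the one the protocol regards as no longer used to bladder filling and emptying.

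**Working it through.** The plan gives no figure to reproduce here. The check sets the sections side by side and then counts.

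**Step 1. Which halting events fall inside the exemption?**

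| Event | Counts under 6.3? | Reported under 6.1 and 6.1.1? |
|---|---|---|
| Any Table 2 event graded severe, not serious, at least possibly related | Yes, as a severe event | No |
| Accidental removal, if the catheter is meant | Yes, as the first listed clinically significant event | No |
| Table 2 event judged serious | Yes, through the serious-event trigger if at least possibly related | Yes, within 24 hours under 6.2 |
| Non-solicited adverse event | Yes, if severe or listed, and at least possibly related | Yes |

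All 6 of the 6 Table 2 rows are exempt, and any of them could fall in the first line of the table. Bladder discomfort is the clearest case, because Appendix A defines its severity grades in terms of discomfort. Of the 3 clinically significant events in 6.3, 1 (dislodgement) has a natural match in Table 2. Table 2 labels five rows as possibly related and the sixth as related. Relatedness will therefore often be met, although it remains a judgement for each case.

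**Step 2. Does another written route bring these events to the Chief Investigator?**

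- *The 24-hour route in 6.2* covers serious events only. The solicited serious events listed under 6.1.3 do not include the Table 2 events, so a Table 2 event judged serious is reported. One that is severe but not serious is not.
- *Causality assessment.* Section 6.1 gives causality to the Chief Investigator, but the item follows the statement about reporting non-solicited events. Even if it covers every adverse event, it sets no time limit. Appendix A gives causality to the investigator caring for the participant and adds: "If any doubt about the causality exists, the local investigator (PI) should inform the Chief Investigator". A clear-cut case need not be passed on.
- *Section 6.1.2* prescribes actions for the individual participant: stop using the valve, revert to usual care, withdraw on recurrence. None of these feeds a study-level count.
- *The interim review* in section 5 looks at all safety data, but only for the first 4 participants.

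**Step 3. How much of the study follows the interim review?**

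- Participants: 16 − 4 = 12, and 12/16 = 75%. These are the remaining 4 of Group 1 and all 8 of Group 2.
- Visits: 16 × 2 = 32, which agrees with the 32 pads in section 5.2.5. After the review there are at most 12 × 2 = 24, and 24/32 = 75%. The number is lower if a participant stops on Day 1.

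These shares describe how much testing takes place without a scheduled review. They do not estimate the chance of a missed halt. The protocol gives no event rate and none is assumed.

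**The case against.** The strongest reply is that the two sections can both be obeyed. Section 6.3 is triggered by events, not by reported events, and 6.1.1 lifts only the duty to report. Every adverse event is still recorded and categorised by severity and relatedness, the two attributes the halting rule uses. Section 6.1 sets no deadline for any non-serious event, so the lack of one is not peculiar to solicited events. Local procedures, site SOPs and the monitoring plan may provide for escalation. The object of accidental removal is not stated and could be the valve. Visits are supervised and last at most 7 hours. If discomfort occurs and the valve does not open on straining, it is disconnected and that participant stops.

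Much of this stands. The data will exist, the practical risk is reduced, and the accidental removal overlap is an inference. The reply does not close the gap, for three reasons:

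- Recording an event does not tell whoever applies the rule that it has occurred. In 6.1 the Chief Investigator is the only named recipient of an adverse event report, so the exemption cannot safely be read as covering external reporting alone.
- Procedures that are not shown cannot be assumed to override an exemption stated in the protocol.
- Severe, non-serious bladder discomfort falls under both sections, whatever accidental removal means.

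**Conclusion.** The concern holds. As written, 6.1.1 works against the adverse event trigger in 6.3. The gap is confined to solicited events that are severe or listed as clinically significant but are not serious; serious ones go through 6.2. It lies in prompt notification, since the events are still recorded. All six Table 2 events are exempt without a severity limit, and 12 of 16 participants (75%) are tested after the only safety review the protocol schedules.

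The severe-event conflict follows directly from the text. The dislodgement overlap assumes that accidental removal refers to the catheter, which is the natural reading. How often a halt would be missed cannot be estimated from the protocol. This should be corrected: a first-in-human halting rule ought not to depend on staff looking past a written exemption.

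**What to change.** Add one sentence to section 6.1.1:

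*Any adverse event that is severe, or is listed as clinically significant in section 6.3, is reported to the Chief Investigator on the Adverse Events form within 24 hours, even if it appears in Table 2, and, if assessed as at least possibly related, is counted towards the halting rule in section 6.3.*

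The 24 hours is a proposal taken from the protocol's own period for serious events in 6.2. Relatedness remains a case-by-case assessment, and mild or moderate Table 2 events not listed in 6.3 stay exempt. The wording and threshold of 6.3 do not change.

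The cost is one sentence and a few extra forms. Trial procedures and sample size are unaffected.
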